8.1.8 ELECTROCARDIOGRAMS

- Electrocardiograms (12-lead) will be recorded after the participants have been supine for 5 minutes. Standard ECG parameters including heart rate, QRS, PR, QT, and QTc intervals will be measured. The ECGs will be read by a study physician to assess for any abnormalities. Abnormal ECG parameters include, but are not limited to ventricular hypertrophy, left axis deviation, atrial or ventricular arrhythmias other than sinus, and prolonged QTc (greater than 500 ms). ECGs may be repeated if data quality is compromised due to poor lead placement or machine error.
- Confirmed ECG anomalies will be referred for appropriate medical follow-up.

8.1.9 BLOOD FOR PK/HACA AND CYTOKINES

- PK of IXT-m200: A validated enzyme linked immunosorbent assay procedure will be used to quantitate IXT-m200 in serum samples. Approximately 1 mL per sample is required.
- HACA: A validated electrochemiluminescent procedure has been developed to quantitate HACA in serum samples. Approximately 1 mL per sample is required. These samples may be analyzed after the completion of this study.
- Cytokine panel to include at a minimum IL-6, IL-8, and TNF α levels will be determined only if any study drug infusion reaction occurs.

8.2 ADVERSE EVENTS AND SERIOUS ADVERSE EVENTS

8.2.1 DEFINITION OF ADVERSE EVENTS (AE)

An AE is any untoward medical occurrence in a person administered study drug, whether or not considered intervention-related. An AE can therefore be any unfavorable and unintended sign (including an abnormal laboratory finding), symptom, or disease temporally associated with the use of study drug, whether or not related to the IXT-m200 dose.

The AE may be:

- a new illness;
- worsening of a sign or symptom of the condition under treatment or of a concomitant illness;
- an effect of the study medication, including comparator; or
- a combination of 2 or more of these factors.

No causal relationship with IXT-m200 or with the clinical study itself is implied by the use of the term “AE”. Pre-existing conditions will not be reported as an AE unless there has been a substantial increase in the severity or frequency of the problem which has not been attributed to natural history.

Surgical procedures themselves are not AEs; they are therapeutic measures for conditions that require surgery. The condition for which the surgery is required may be an AE. Planned surgical measures permitted by the clinical study protocol and the condition(s) leading to these measures are not AEs.

Adverse events fall into the categories “nonserious” or “serious”.

8.2.2 DEFINITION OF SERIOUS ADVERSE EVENTS (SAE)

An SAE is an AE that at any dose:

- results in death;
- is life-threatening;
- requires hospitalization or prolongation of existing hospitalization;
- results in persistent or significant disability/incapacity; or
- is a congenital anomaly/birth defect.

The term “life-threatening” in the definition of “serious” refers to an event in which the person was at immediate risk of death at the time of the SAE; it does not refer to an SAE which hypothetically might have caused death if it were more severe.

Medical and scientific judgment will be exercised in deciding whether other AEs, such as important medical events that may not be immediately life-threatening or result in death or hospitalization but may jeopardize the person or may require intervention to prevent one of the other outcomes listed above. These will also usually be considered serious.

8.2.3 CLASSIFICATION OF AN ADVERSE EVENT

8.2.3.1 SEVERITY OF EVENT

The general approach outlined by the Club Phase 1 working group in the British Journal of Clinical Pharmacology² will be used to categorize the severity of all AEs. The stopping rules outlined in Section 7.1 will apply.

The following criteria will be used:

- Grade 1: Transient or mild discomfort; does not interfere with daily activity; no medical intervention/treatment required,
- Grade 2: Mild to moderate limitation in activity, some assistance may be needed; no or minimal intervention/treatment required, including but not limited to mild analgesics, antacids or antibiotics,
- Grade 3: Marked limitation in activity, some assistance usually required; medical intervention/treatment required,
- Grade 4: Extreme limitation in activity, significant assistance required; significant medical intervention/treatment, likely requiring hospitalization.

For example, if hypotension is not immediately responsive to medications, this will constitute a Grade 3 reaction and it will be documented as such. Similarly, if bronchospasm ($\text{SaO}_2 < 93\%$ on oxygen) occurs and requires medications, this will constitute a Grade 3 reaction, and will be documented as such.

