2.2.1.2 SPECIFIC IXT-M200 POTENTIAL RISKS

During the Phase 1 study of IXT-m200, there were no SAEs or discontinuations due to treatment-emergent AEs. Overall, 90% of participants experienced at least 1 AE, but there were no apparent trends in the frequency, relatedness, or severity of AEs with increased dose or between active- and placebo-treated participants¹.

There were 3 adverse events in 2 subjects that were attributed to IXT-m200. A mild infusion reaction (CTCAE v.4.0 Grade 3) and bronchospasm (Grade 2) occurred in the same subject. The symptoms included a brief period of bronchospasm with no drop in oxygen saturation that resolved with stopping the infusion. A separate subject experienced an AE of mild proteinuria (Grade 1). Both subjects were in the same dose group (2 mg/kg IXT-m200).

The most frequently reported AEs were increased blood creatine phosphokinase, upper respiratory tract infection, decreased hemoglobin, headache, increased aspartate aminotransferase (AST) and alanine aminotransferase (ALT), proteinuria, decreased white blood cell (WBC) count, and nasal congestion.

Because IXT-m200 is a mouse-human chimeric antibody, the potential for a human anti-chimeric antibody (HACA) response exists. Following single doses of IXT-m200, only 4 of 32 participants were confirmed positive for HACA in the Phase 1 study. The development of HACA did not appear to be dose-related.

In the Phase 2a STAMPOUT study, all AEs were grade 1 or grade 2. Common AEs included palpitations, tachycardia, dry mouth, nausea, injection site pain, headache, euphoria, hypervigilance, and hyperhidrosis. All of these AEs are expected in people receiving METH, and all participants in this study received METH. Of these, only blurred vision, nausea, feeling abnormal, and dry mouth were probably related to IXT-m200; each AE was reported by only one subject who received IXT-m200. Furthermore, none of the AEs associated with METH appeared to be exacerbated by IXT-m200. For example, an analysis of heart rate changes following METH administration demonstrated that average percent heart rate increase, and average peak heart rates were not changed in the presence of IXT-m200. Plus, the individual maximum attained heart rate in each group was 139 (placebo), 142 (6 mg/kg), and 144 (20 mg/kg).

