9.2 SAMPLE SIZE DETERMINATION

The sample size chosen for this study is not based on statistical considerations. The number of subjects within each dose group was chosen based on historical experience with safety and tolerance trials and to match the study design used in the previous Phase 1 study with IXT-m200 which provided adequate safety and pharmacokinetic data. The sample size falls within the range of those used in other studies of this nature.

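### Does the change of severity scale since the earlier Phase 1 study make the SAP 6.3 severity table misleading?

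*Protocol*

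**What the plan says.** Protocol 8.2.3.1 applies one scale to all adverse events: the Club Phase 1 working group approach, with a printed list of four grades. The lowest reads "Grade 1: Transient or mild discomfort; does not interfere with daily activity; no medical intervention/treatment required". Grade 2 covers mild to moderate limitation with "no or minimal intervention/treatment required, including but not limited to mild analgesics, antacids or antibiotics". The third reads "Grade 3: Marked limitation in activity, some assistance usually required; medical intervention/treatment required". Two illustrations follow. In the second, bronchospasm with saturation below 93% on oxygen that "occurs and requires medications, this will constitute a Grade 3 reaction, and will be documented as such". Protocol 7.1 uses the same grades for the enrolment pause, and SAP 6.3 tabulates treatment-emergent events by Grades 1 to 4, counting the worst. SAP 6.3 does not name the scale.

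On the earlier Phase 1 study, protocol 2.2.1.2 reports: "A mild infusion reaction (CTCAE v.4.0 Grade 3) and bronchospasm (Grade 2) occurred in the same subject". It adds: "The symptoms included a brief period of bronchospasm with no drop in oxygen saturation that resolved with stopping the infusion". Its overall reading was that "there were no apparent trends in the frequency, relatedness, or severity of AEs with increased dose". Protocol 9.2 says group sizes were chosen from experience and "to match the study design used in the previous Phase 1 study with IXT-m200 which provided adequate safety and pharmacokinetic data".

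**The concern.** The only Grade 3 event attributed to the drug sits on CTCAE v4.0, and this trial uses another list with no bridge between them. The description of the earlier reaction (brief, no desaturation, over once the infusion stopped) does not meet the protocol's Grade 3 bronchospasm example. The printed list also does not say whether stopping an infusion counts as no, minimal or medical intervention, or whether one element of a grade is enough.

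The trial goes from 20 mg/kg to about 40 mg/kg. If the same reaction recurred and was graded 1 or 2, the table would show no Grade 3 event where the earlier study showed one. A reader might take a change of scale for reassurance at the higher dose. The same reaction in two participants might or might not count toward the pause in 7.1. A related worry is that the list turns on discomfort, activity, assistance and intervention, so an untreated, symptomless laboratory or ECG finding meets no printed element of Grade 3 or 4.

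**Working it through.** The plan gives no power, alpha or rate on this point. The check therefore compares the texts and then sizes the effect.

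**1. Denominators.** Protocol 2.1.4: 42 dosed, 10 on placebo, so 42 − 10 = 32 active. The printed antibody figure confirms this: 4/32 = 12.5%. Here, 7:2 allocation of about 9 participants gives 7 active.

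**2. Which event carried which grade.**

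| Event in the same subject | Earlier study | Protocol 8.2.3.1 |
|---|---|---|
| Infusion reaction | CTCAE v4.0 Grade 3, also described as mild | No worked example; general criteria apply |
| Bronchospasm | Grade 2 | Example of Grade 3: saturation below 93% on oxygen and medication required |

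The earlier bronchospasm had no drop in saturation, so it misses this Grade 3 example. It was graded 2, so the two agree. The infusion reaction was the event graded 3, and the bronchospasm example does not describe it.

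**3. Whether the example sets the boundary.** It is offered as an illustration, so meeting it is sufficient for Grade 3 but not necessary. The general Grade 3 criterion has no saturation element. The documents do not report how far the subject's activity was limited or whether medication was given. On the printed list the infusion reaction could be Grade 1, 2 or 3, and a downgrade is possible but not shown.

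**4. What is matched to the earlier study.** Protocol 9.2 and SAP 2.3 speak of group numbers and study design. The earlier study averaged 42/5 = 8.4 participants per group, with 10/5 = 2 on placebo. This trial has about 9, with 2 on placebo. Nothing is said about a common grading scale.

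**5. Chance of recurrence among 7 active participants.** With rate p, P(at least one) = 1 − (1 − p)^7, and P(at least two) = 1 − (1 − p)^7 − 7p(1 − p)^6.

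| Rate p | At least one | At least two |
|---|---|---|
| 1/32 = 3.1% | 19.9% | 1.8% |
| 16.2% (upper exact 95% limit for 1/32; lower limit 0.1%) | 71.0% | 31.8% |
| 1/68, adding 0 of 36 active from STAMPOUT (scale not named) | 9.85% | 0.4% |

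The rate at 3 g is unknown. Assumed rates of 10% to 40% would give 15% to 84% for at least two, but nothing in the documents supports a particular value in that range.

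**6. Effect of one regrade.** The earlier study's related Grade 3 count would go from 1/32 (exact 95% CI 0.1% to 16.2%) to 0/32 (upper limit 1 − 0.025^(1/32) = 10.9%). For no event in 7, the upper limit is 1 − 0.025^(1/7) = 41.0%. The imprecision of a 7-participant arm far exceeds the effect of the scale.

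**7. Which outputs depend on grade.** The primary endpoint counts participants with treatment-related events and does not use grade. The tables by system organ class, preferred term and relationship do not use it either. The severity table does, but it compares IXT-m200 with placebo inside this trial, on one scale.

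**The case for a change.** The best case for a change has four parts.

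First, the SAP prevails over the protocol where they differ (protocol 9), and CTCAE is the only severity scale its text names, so a reader might take the SAP 6.3 grades as CTCAE. But SAP 1.3 uses that name only for the earlier study, and saying nothing about the scale is not a difference. The SAP states that it rests on the protocol, whose four grades it repeats. Naming the scale would be tidier, but it would change no number.

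Second, severity against known risk is used elsewhere: the expectedness test in protocol 8.2.3.3 and the unanticipated-problem test in 8.3.1. This is a fair point. Those, however, are judgements on individual cases, made with the clinical description of the earlier reaction to hand. They do not draw on the severity table.

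Third, the ambiguity about a stopped infusion reaches the 7.1 pause. That stands as missing detail. Sections 7.1 and 8.2.3.1 agree on the scale, and 2.2.1.2 reports another study on another scale, so the sections do not contradict one another. Grade is a clinician's assessment (8.2.4). Infusion reactions also have handling that does not depend on grade: discontinuation is possible under 7.2, cytokine sampling is scheduled, and SAP 6.5 provides a listing and narrative if cytokines are measured. The sponsor may also suspend the study at its discretion (10.1.2).

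Fourth, laboratory findings make up 6 of the 9 event terms listed as most frequent earlier, and the list fits them poorly. Whether the cited scale covers them cannot be settled from these documents, and no event is shown to be misgraded.

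**Conclusion.** The facts hold: the scales differ, no bridge is given, and SAP 6.3 leaves its scale unnamed. The inference that the severity table is misleading does not hold. If an identical reaction recurred, a table showing no worsening in severity would be correct, because an identical reaction is not worse. A rise in frequency would still show by preferred term and relatedness. The earlier Grade 3 reaction occurred at 2 mg/kg, not at the top dose, so it is not evidence of a trend that a change of scale could hide.

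The unnamed scale is a gap that an analyst fills from protocol 8.2.3.1. Adding a second CTCAE grade would serve a cross-study severity comparison that the plan does not make, and no planned result would change. The description of the earlier Grade 3 reaction as mild is an oddity in the account of a finished study and has no bearing on this analysis.

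The size is small: 1.8% for two recurrences in 7 at the documented rate, and a shift from 1/32 to 0/32 set against an interval of 0% to 41.0% for no events in 7. This assumes that the earlier rate is a fair guide to 3 g, which the documents cannot establish, and that clinicians apply the printed list consistently. Anyone who later sets the two studies side by side should remember that their grades are not interchangeable.

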8.2.3.2 RELATIONSHIP TO STUDY INTERVENTION

All adverse events (AEs) must have their relationship to study intervention assessed by the clinician who examines and evaluates the participant based on temporal relationship and his/her clinical judgment. The degree of certainty about causality will be graded using the categories below. In a clinical trial, the study product must always be suspect.

DEFINITELY – The AE:

- is clearly related to the investigational agent or research intervention;
- has a temporal relationship to the administration of the study drug;
- follows a known pattern of response;
- occurs in the absence of an alternative cause.

PROBABLY – The AE:

- follows a reasonable temporal sequence from study drug administration;
- abates upon discontinuation of the drug;
- cannot be reasonably explained by the known characteristics of the participant's clinical state.

POSSIBLY – The AE:

- follows a reasonable temporal sequence from study drug administration;
- could have been produced by the participant's clinical state or by other modes of therapy administered to the participant.

UNLIKELY – The AE:

- does not follow a reasonable temporal sequence from study drug administration;
- is readily explained by the participant's clinical state or by other modes of therapy administered to the participant.

UNRELATED – The AE:

- is definitely produced by the participant's clinical state or by other modes of therapy administered to the participant.

8.2.3.3 EXPECTEDNESS

The Sponsor will be responsible for determining whether an AE is expected or unexpected. An AE will be considered unexpected if the nature, severity, or frequency of the event is not consistent with the risk information previously described for the study agent.

8.2.4 TIME PERIOD AND FREQUENCY FOR EVENT ASSESSMENT AND FOLLOW-UP

The occurrence of an AE or SAE may come to the attention of study personnel during study visits and interviews of a study participant presenting for medical care, during engagement of the participant with the smartphone app, or upon review by a Study Monitor. All AEs including local and systemic reactions not meeting the criteria for SAEs will be captured on the appropriate CRF. Information to be collected

includes event description, time of onset, clinician's assessment of severity, relationship to study product (assessed only by those with the training and authority to make a diagnosis), and time of resolution/stabilization of the event. All AEs occurring while on study must be documented appropriately regardless of relationship. All AEs will be followed to adequate resolution.

Any medical condition that is present at the time that the participant is screened will be considered as baseline and not reported as an AE. However, if the study participant's condition deteriorates at any time during the study, it will be recorded as an AE.

Changes in the severity of an AE will be documented to allow an assessment of the duration of the event at each level of severity. All AEs characterized as intermittent require documentation of onset and duration of each episode.

The Investigator will record all reportable events with start dates occurring any time after informed consent is obtained until the last day of study participation. At each study visit, the Investigator will inquire about the occurrence of AE/SAEs since the last visit. Events will be followed for outcome information until resolution or stabilization.

8.2.5 ADVERSE EVENT REPORTING

All AEs (whether serious or nonserious) that occur after the participant has been randomized into a treatment group must be documented on the appropriate pages of the CRF. For all AEs, the Investigator will provide an assessment of the AE, its treatment and resolution, and its relationship to IXT-m200. Every attempt should be made to describe the AE in terms of a diagnosis. If appropriate, component symptoms should also be listed below the diagnosis. If only nonspecific signs or symptoms are present, then these should be recorded as a diagnosis.

All participants who have AEs, whether considered associated with the use of IXT-m200 or not, will be monitored to determine the outcome. The clinical course of the AE will be followed up according to accepted standards of medical practice, even after the end of the period of observation to a maximum of 30 days following the end of study visit. Should the AE result in death, a full pathologist's report should be supplied, if possible.

8.2.6 SERIOUS ADVERSE EVENT REPORTING

The Investigator will complete an SAE form within the following timelines:

- All deaths and immediately life-threatening events, whether related or unrelated, will be recorded on the designated SAE form and submitted to the Sponsor within 24 hours of site awareness.
- Other SAEs regardless of relationship, will be submitted to the Sponsor within 72 hours of site awareness.

All SAEs will be followed until satisfactory resolution or until the site Investigator deems the event to be chronic or the adherence to be stable. Other supporting documentation of the event may be requested by the Sponsor and should be provided as soon as possible.

Information not available at the time of the initial report will be documented on a follow-up SAE form. SAE information previously sent to the Sponsor will not be duplicated. When a nonserious event becomes serious, details will be forwarded immediately to the Sponsor on the designated SAE report form.

The study Sponsor will be responsible for notifying the Food and Drug Administration (FDA) of any unexpected fatal or life-threatening suspected adverse reaction as soon as possible, but in no case later than 7 calendar days after the sponsor's initial receipt of the information. In addition, the Sponsor must notify FDA and all participating Investigators in an Investigational New Drug (IND) safety report of potential serious risks, from clinical trials or any other source, as soon as possible, but in no case later than 15 calendar days after the sponsor determines that the information qualifies for reporting.

The NIDA Project Officer (PO) will be notified by the Sponsor within 72 hours of the SAE occurrence, and also via NIDA's online Serious Adverse Event Tracking and Reporting System (SAETRS).

8.2.7 REPORTING EVENTS TO PARTICIPANTS

It is not anticipated that safety updates, including AEs or SAEs, will be reported to study participants.

8.2.8 EVENTS OF SPECIAL INTEREST

Not applicable.

8.2.9 REPORTING OF PREGNANCY

If a participant is found to be pregnant after they have received study drug, they should complete the study, with no further study drug doses administered, and be followed to determine the outcome of the pregnancy if the participant is willing. Generally, follow-up will be no longer than 6 to 8 weeks after the estimated delivery date. While pregnancy itself is not considered an AE or SAE, any pregnancy complications will be recorded as an AE or SAE.

Pregnancies should be reported by the Investigator to the Sponsor within 2 days of identification.

8.3 UNANTICIPATED PROBLEMS

8.3.1 DEFINITION OF UNANTICIPATED PROBLEMS (UP)

Unanticipated problems involving risks to participants or others will include, in general, any incident, experience, or outcome that meets all of the following criteria:

- Unexpected in terms of nature, severity, or frequency given (a) the research procedures that are described in the protocol-related documents, such as the IRB-approved research protocol and informed consent document; and (b) the characteristics of the participant population being studied;
- Related or possibly related to participation in the research (“possibly related” means there is a reasonable possibility that the incident, experience, or outcome may have been caused by the procedures involved in the research); and
- Suggests that the research places participants or others at a greater risk of harm (including physical, psychological, economic, or social harm) than was previously known or recognized.

